3.2.2 Secondary outcomes

Immunogenicity

Functional antibody – All samples at all timepoints will be assayed using the GenScript cPass SARS-CoV-2 Neutralization Antibody detection kit for both WT and Delta variant RBD antigen.

Neutralizing antibody - A fraction of samples (20%) will be assessed using a SARS-CoV-2 microneutralisation assay undertaken at the PDI, Melbourne. Assays will be done at all four timepoints to the WT (vaccine) strain and for 2 Variants of concern.

Cellular immunity - Cellular immunity will be assessed on a subset of 40% of participants, with samples collected at three timepoints: baseline, 28 days, and 12-months post-vaccination as follows:

- *QuantIFERON Human IFN- γ SARS-CoV-2* (Qiagen) will be performed using heparinised whole blood
- Peripheral blood mononuclear cells (PBMCs) will also be isolated by density gradient centrifugation within 12 hours of collection and stored in liquid nitrogen at MCRI. Assays performed will include IFN- γ Elispot, intracellular cytokine assays (flow cytometry) and multiplex cytokine assays.

Safety

- All solicited adverse events (AE) will be collected for 7 days, all unsolicited AE will be collected for 28 days, and all medically attended AE will be collected for 3 months. SAE will be collected throughout the follow up period of 12 months

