7 TRIAL VISITS AND PROCEDURES

7.1 Schedule of assessments

	Visit 1 (day 0)	Visit 2 (day 1)	Visit 3 (day 7)	Visit 4 (day 28)	Visit 5 (3 mths)	Visit 6 (6 mths)	Visit 7 (12 mths)
Timing	Day 0	Day 1	Day 7	Day 28	3 months	6 months	12 months
Visit window			+ 3 days	+ 7 days	+/- 14 days	+/- 14 days	+/- 14 days
Informed consent	X						
Eligibility confirmation	X						
Randomisation	X						

Blood sampling	X			X		X	X
Vaccination	X						
Vital signs	X						
Issue diary card, ruler and thermometer	X						
Collect diary card			X				
Documentation of Solicited AE	X	X	X				
Documentation of unsolicited AE	X	X	X	X			
Documentation of medically attended AE	X	X	X	X	X		
Documentation of SAE	Throughout study period						
Documentation of confirmed COVID-19 infection	Throughout study period						

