7.2 Description of procedures

7.2.1 Visit 1 (Day 0)

Informed consent must be signed by both participant and study doctor or nurse.

Participant eligibility must be confirmed prior to randomisation and on the same date as administration of the investigational product.

Eligibility must be confirmed by a study doctor or study nurse. Randomisation must be completed by the unblinded vaccinator who will document the participant's randomisation number on the enrolment log.

Study staff will administer a Visit 1 questionnaire documenting demographic information, height and weight, dates and type of primary COVID-19 vaccine, any comorbidities and concomitant medication.

The following vital signs will be recorded by a study doctor or study nurse prior to vaccination: temperature, pulse rate, respiratory rate, and blood pressure.

Prior to vaccination, for all participants, 5mL of blood will be collected and processed according to the SOP. CMI participants will have an additional 25ml collected and processed for Quantiferon analysis and PBMC separation and storage.

Following randomisation, the unblinded vaccinator will administer the applicable vaccine to the participant.

The following vital signs will be recorded by a study doctor or study nurse 15 minutes following vaccination: temperature, pulse rate, respiratory rate, and blood pressure.

Study staff will provide participant with reactogenicity diary card and instruct the participant on how to complete the diary card up to and including 7 days following vaccination.

Study staff will provide the participant with a thermometer and ruler and detailed instructions on how to use these for measuring temperature and potential erythema and induration. Study staff will provide the participant with a schedule of visit appointments and instruct the participant on how to contact the study staff in case of any SAE or symptoms suggestive of COVID-19.

Study staff will keep the participant under observation for minimum 15 minutes and document any immediate adverse events.

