7.2.4 Visit 5 (3 Months)

Study staff will contact the participant by phone and document information on any medically attended AE or SAE.

Study staff will also document any new information regarding unsolicited adverse events with onset up to 28 days following vaccination, such as resolution.

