7.2.5 Visit 6 (6 Months)

For all participants, 5mL of blood will be collected in an SST tube. For participants in the CMI subset, 3mL of blood for Quantiferon test will be collected in a heparinised tube, and 20mL of blood for PBMC will be collected in a heparinised tube. Blood samples will be kept at room temperature and transferred to the laboratory within 3 hours of collection.

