7.2.6 Visit 7 (12 Months)

For all participants, 5mL of blood will be collected in an SST tube. For participants in the CMI subset, 3mL of blood for Quantiferon test will be collected in a heparinised tube, and 20mL of blood for PBMC

will be collected in a heparinised tube. Blood samples will be kept at room temperature and transferred to the laboratory within 3 hours of collection. Participants who complete the 12-month study period will receive a gift. If they request, results of their tests will be shared and discussed with them by a member of the study team.

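### The last enquiry about medically attended adverse events may be made 14 days before the stated 3-month period ends, and no later visit catches up

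*Combined protocol and SAP*

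**What the plan says.** - **Period.** Section 3.2.2 (and the synopsis) states that "all medically attended AE will be collected for 3 months", and for serious events that "SAE will be collected throughout the follow up period of 12 months".
- **Schedule.** In 7.1 the row "Documentation of medically attended AE" is marked at Visits 1 to 5 and is blank at Visits 6 and 7. The rows for serious adverse events (SAEs) and for confirmed COVID-19 each read "Throughout study period".
- **Windows.** Also in 7.1, Visits 3 and 4 have late-only windows (+3 and +7 days). Visits 5, 6 and 7 have two-sided windows of 14 days.
- **Visit 5 (7.2.4).** "Study staff will contact the participant by phone and document information on any medically attended AE or SAE". The same section also asks for updates on unsolicited events that began within 28 days.
- **Visit 6 (7.2.5).** The text begins "For all participants, 5mL of blood will be collected in an SST tube" and deals only with collecting and handling blood.
- **Visit 7 (7.2.6).** Blood collection again, then "Participants who complete the 12-month study period will receive a gift" and an offer to share test results.
- **Participant reporting (7.2.1, Visit 1).** Staff "instruct the participant on how to contact the study staff in case of any SAE or symptoms suggestive of COVID-19".

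**The concern.** A fixed collection period is covered for everyone only if the last enquiry falls on or after its final day, or if a later contact picks up what was missed. The plan does this for the shorter periods. The 7-day and 28-day periods close at visits that cannot be early, and the next contact (Visit 4 for solicited events, Visit 5 for unsolicited events) asks for new information with an explicit onset limit. For medically attended events neither safeguard is present: the closing call may be early, and Visit 6 does not return to the subject. The Visit 5 question also has no onset limit, so a late call can take in events from after 3 months.

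What is at stake is the secondary objective in 3.1.2 on the safety of the booster regimens. A medically attended event rate labelled as 3-month would come from participants observed for unequal times, some of them for less than 3 months.

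**Working it through.** The plan gives no figure to reproduce here; the check is calendar arithmetic.

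**Inputs**
- Collection period: 3 months (3.2.2). The plan does not convert this to days. I take 91 days, with a range of 84 to 92 by month convention (assumption).
- Visit 5 window: 14 days either side (7.1).
- Last scheduled enquiry about medically attended events: Visit 5 (7.1, 7.2.4).

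**Worst case for one participant**
- Earliest permitted call = nominal day − 14 = 91 − 14 = day 77 (range day 70 to 78).
- Share of the period not asked about = 14/91 = 15.4% (14/84 = 16.7%; 14/92 = 15.2%).

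**Average, if calls are spread evenly over the window (assumption)**
- Permitted days: 14 + 1 + 14 = 29.
- Share called early = 14/29 = 48%.
- Mean loss over all participants = (1 + 2 + … + 14)/29 = 105/29 = 3.6 days, and 3.6/91 = 4.0%.
- The true average depends on when calls are made. It is 0 if nobody is called early and 14 days if everyone is called on the first permitted day.

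**The late side**
- Latest permitted call = 91 + 14 = day 105. With no onset limit in 7.2.4, up to 14 extra days can be recorded for some participants.

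**Is the gap closed elsewhere?**
- Visit 6: no mark in 7.1 and no question in 7.2.5.
- Participant-initiated reporting: the Visit 1 instruction covers SAEs and COVID-19 symptoms, not other medically attended events.
- Section 8.2 sets out solicited, unsolicited and serious events and does not mention medically attended ones.
- A medically attended event that is also serious is still within SAE collection, so the gap concerns non-serious events only.

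**The same test for SAEs**
- Earliest Visit 7 = 365 − 14 = day 351, and 14/365 = 3.8%. Here the gap is closed on paper: the SAE row in 7.1 is not tied to a visit date, 8.2 follows SAEs for as long as the trial runs, and participants have been told how to report them.

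**The case against.** The strongest reply is that the effect is small and largely manageable. The 15% applies only to someone called exactly 14 days early, the average under an even spread is about 4%, and serious events are caught by another route. Section 8.3 records onset dates, so an analyst can cut off events collected after 3 months without a protocol change. All of this stands. The onset date does not help with the early side, however: an event nobody asked about has no record to truncate.

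A reader might infer three stronger things, and the documents do not support them.

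- **That the 12-month SAE period is not covered because Visits 6 and 7 contain no safety question.** The visit descriptions are silent, but 7.1 schedules SAE and COVID-19 documentation across the whole study, 8.2 agrees, and the trial ends only with the last assay (7.2.11). The case report forms and data management plan are not in view, so silence in a short visit description does not show that nobody asks. What remains is a mismatch between 7.1 and 7.2.5–7.2.6 that needs reconciling.
- **That arms will be under-counted unequally because allocation is disclosed at day 28.** The windows and instructions are the same in every arm, and nothing in the plan shows differential reporting.
- **That the Visit 7 window should become late-only too.** That visit is also the 12-month blood draw. The change would cut its window from 29 to 15 days and, with visits spread evenly, move mean sampling about 7 days later, for little gain given continuous SAE documentation.

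**Conclusion.** The concern holds for medically attended events. The plan states a 3-month collection period but permits its last enquiry on about day 77 and provides no catch-up. For participants called early, up to 14 of about 91 days of non-serious medically attended events are not asked about. That is 15% at worst (15–17% across month conventions), and about 3.6 days or 4% on average if calls are spread evenly over the window. The worst case rests only on the stated window and the day count for 3 months; the average rests on the assumed spread.

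This is a minor point. It concerns the completeness of one secondary safety outcome, affects all arms alike by design, and does not touch the day-7 and day-28 primary outcomes. For SAEs and confirmed COVID-19 the point is only that the visit descriptions should match the schedule.

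**What to change.** 1. Close the gap in one of two ways:
   - in 7.1, change the Visit 5 window to 0/+14 days; or
   - keep the window and add to Visit 6 (7.2.5) a question about medically attended events with onset up to 3 months that have not yet been reported.
2. In either case, state the nominal 3-month date in days and count only medically attended events with onset up to that date.
3. Reconcile 7.2.5 and 7.2.6 with 7.1 by listing the SAE and confirmed COVID-19 questions at Visits 6 and 7.

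**Cost.** The first option narrows the window for one phone call from 29 to 15 days; no blood is drawn at that contact, so no sampling time moves. The second adds one question at a visit that already takes place, with a longer recall interval for the participant. Items 2 and 3 are wording changes and add no visit or sample.

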4 TRIAL DESIGN

4.1 Overall design

This clinical trial will be a single blind, randomised study to determine the immunogenicity and reactogenicity of booster doses of SARS-CoV-2 vaccines in adults. Both fractional and standard doses will be tested.

The groups are described below. The trial intervention will be a single booster dose of vaccine: -

Primary vaccine	Booster vaccines
Pfizer-BioNTech (BNT162b2, or Comirnaty [®])	1. Pfizer-BioNTech (BNT162b2, or Comirnaty [®]) Standard dose
	2. Pfizer-BioNTech (BNT162b2, or Comirnaty [®]) Fractional dose
	3. Moderna (mRNA-1273, or Spikevax [®]) Standard Dose
	4. Moderna (mRNA-1273, or Spikevax [®]) Fractional Dose
AstraZeneca (ChAdOx1-S, or Vaxzevria [®])	5. Pfizer-BioNTech (BNT162b2, or Comirnaty [®]) Standard Dose
	6. Pfizer-BioNTech (BNT162b2, or Comirnaty [®]) Fractional Dose
	7. Moderna (mRNA-1273, or Spikevax [®]) Standard Dose
	8. Moderna (mRNA-1273, or Spikevax [®]) Fractional Dose

The trial intervention will be given 6-9 months after the primary vaccine. This is in line with ATAGI recommendations for booster vaccine doses which allows booster doses from 5 months onwards (2). The groups size will be 100 individuals with an even spread of participants above and below 50 years in each group. The trial will be single site.

The trial will be single blind. The participants and those evaluating reactogenicity will be blinded to the vaccine allocation for the first 28 days following vaccination. After that, both the clinical investigators and potentially participants will be aware of their investigational product allocation. Immunologists and laboratory staff will remain blinded to the investigational product allocation.

4.2 Justification for dose

This project is designed to evaluate the potential use of fractional dose and heterologous booster regimens for individuals who have previously received two doses of Covid-19 vaccine. The fractional dose has advantages for the individual and the broad community. At an individual level, the likelihood of moderate adverse reactions is reduced by the use of a fractional dose. Existing data suggests that immunogenicity and effectiveness will be maintained, but this will be evaluated early in the project and if immunogenicity proves to be inadequate this will be addressed according to the recommendations of the DSMB. At a national and global level, the approach carries the potential to greatly expand the availability of Covid-19 vaccine, helping to correct the inequity that currently characterises the global Covid-19 situation.

4.3 Trial population

The trial population will be adults 18 years and older who have received two doses of Covid-19 vaccines, either Pfizer-BioNTech (BNT162b2, *Comirnaty*[®]) or AstraZeneca (ChAdOx1-S, *Vaxzevria*[®]) within the previous 6 to 9 months. There will be no upper age limit.

Procedures will be implemented to ensure participants of all ages (aged 18 and above) are included and that there is an even age distribution in each group.

4.4 Eligibility criteria

If informed consent is granted, study staff will ensure that all the eligibility criteria are met. Potential participants must meet all the inclusion criteria and none of the exclusion criteria to be eligible.

4.4.1 Inclusion criteria

Each participant must meet all the following criteria to be enrolled in this trial:

1. Have completed two doses of Pfizer-BioNTech or AstraZeneca vaccines with the recommended schedule 6 months prior to the date of enrolment
2. Willing and able to give written informed consent
3. Aged 18 years or above
4. Willing to complete the follow-up requirements of the study

Note that subjects with comorbidities other than those listed below as contraindications will be included. Pregnant women or women who may become pregnant will be included.

4.4.2 Exclusion criteria

Potential participant meeting any of the criteria below will be excluded from this trial:

1. Received 3 doses of COVID-19 vaccine
2. Received 2 doses of COVID-19 less than 6 months prior to the start of the trial
3. Received a different Covid-19 vaccine not available in Australia
4. Currently on immunosuppressive medication or anti-cancer chemotherapy
5. HIV infection
6. Congenital immune deficiency syndrome
7. Has received immunoglobulin or other blood products in the 3 months prior to vaccination
8. Study staff and their relatives
9. Have a history of a severe allergic reaction to any COVID-19 vaccines or have a medical exception to receiving further COVID-19 vaccines
10. Cannot read or understand English

4.5 Lifestyle considerations

Not Applicable.

4.6 Screen failures

Screen failures are defined as participants who consent to participate in the trial but are found during screening procedures to be ineligible. They, therefore, do not receive the intervention and are not randomised. We anticipate that there will be very few screen failures due to the minimal inclusion/exclusion criteria.

4.7 Recruitment and identification of potential participants

The study will be advertised across the Melbourne Children’s Campus (MCRI, Royal Children’s Hospital, Royal Melbourne Hospital, Doherty Research Institute), Royal Melbourne Hospital, the Doherty Research Institute, the Parkville precinct and if necessary the broader Melbourne community. Study information (via email, healthcare facilities notice board and/or website/social media etc) will include an information sheet about the study and a link to the study website where they can evaluate their eligibility and obtain additional study details, such as the participant information sheet and consent form (PICF). The potential participant can register their interest and will be given the opportunity to talk with a member of the research team by phone or zoom if they have any further questions. A record of all potential participants will be recorded on a recruitment log. If the potential participant decides not to participate no identifying information will be retained.

4.8 Consent

Informed consent is a process that is initiated prior to the agreement to participate in the trial and continues throughout study participation. Discussion of risks and possible benefits of this vaccination will be provided to the potential participants prior to obtaining informed consent. Trial staff will go through the Informed Consent Form (ICF), which describes in plain language the trial interventions, the study procedures, and the risks and benefits of participation. The ICF will be HREC-approved and the potential participant will be asked to read and review the ICF. The trial staff will then explain the research study further and answer any questions that may arise.

Written documentation of informed consent is required prior to enrolment into the trial. The potential participant will sign and date the final page of the ICF. The trial staff will witness the consent, confirming that the trial has been fully explained and that participant understands the rationale for the trial and the trial processes. The potential participant will be informed that they are free to withdraw from the trial at any time. A copy of the ICF will be given to the potential participant.

5 INTERVENTION

5.1 Treatment arms

Treatment Arms	Route	Dose
1) Pfizer-BioNTech (BNT162b2, or Comirnaty [®])	IM	Standard Dose - (30µg)
2) Pfizer-BioNTech (BNT162b2, or Comirnaty [®])	IM	Fractional Dose - (15µg)
3) Moderna (mRNA-1273, or Spikevax [®])	IM	Standard Dose - (50µg)
4) Moderna (mRNA-1273, or Spikevax [®])	IM	Fractional Dose - (20µg)

5.2 Trial Intervention(s)

Pfizer BioNTech (BNT162b2) BNT162b2 is a lipid nanoparticle-formulated, nucleoside-modified mRNA vaccine that encodes trimerised SARS-CoV-2 spike glycoprotein. BNT162b2 encodes the SARS-CoV-2 full-length spike, modified by two proline mutations to lock it in the prefusion conformation and more closely mimic the intact virus with which the elicited virus-neutralizing antibodies must interact. mRNA vaccines use the pathogen’s genetic code as the vaccine; this then exploits the host cells to translate the code and then make the target spike protein. The protein then acts as an intracellular antigen to stimulate the immune response. The mRNA is then degraded within days. The vaccine RNA is formulated in lipid nanoparticles (LNPs) for more efficient delivery into cells after intramuscular injection.

Moderna (mRNA-1273) COVID-19 Vaccine Moderna (mRNA-1273) encodes the S-2P antigen, consisting of the SARS-CoV-2 glycoprotein with a transmembrane anchor and an intact S1–S2 cleavage site. S-2P is stabilized in its prefusion conformation by two consecutive proline substitutions at amino acid positions 986 and 987, at the top of the central helix in the S2 subunit. The lipid nanoparticle capsule is composed of four lipids and formulated in a fixed ratio of mRNA and lipid.

5.2.1 Description of trial investigational products

5.2.1.1 Trial Products

Active substance	The Pfizer-BioNTech COVID-19 vaccine, BNT162b2, encodes a P2 mutant spike protein and is formulated as an RNA-lipid nanoparticle (LNP) of nucleoside-modified mRNA (modRNA).
Trade or Generic name	Pfizer-BioNTech (BNT162b2, or Comirnaty [®])
Dosage form	Liquid for injection – standard dose is 0.3ml containing 30µg; fractional dose is 0.15ml containing 15ug.
Route of administration	Intramuscular injection
Active substance	The Moderna vaccine, mRNA-1273 encodes the prefusion stabilized S protein of SARS-CoV-2 formulated in RNA-LNPs composed of 4 lipids and 1-monomethoxypolyethyleneglycol-2, 3-dimyristylglycerol with polyethylene glycol.
Trade or Generic name	Moderna (mRNA-1273, or Spikevax [®])
Dosage form	Liquid for injection – standard dose for boosting is 0.25ml containing 50µg; fractional dose is 0.1ml containing 20ug.
Route of administration	Intramuscular injection

5.2.2 Dosage

The standard dose of Pfizer BioNTech COVID-19 vaccine is 30µg contained in 0.3ml of the diluted vaccine and is currently the standard dose that is used for a booster. A half dose is 15 µg contained in 0.15ml of the diluted vaccine. Each pack of the Pfizer BioNTech vaccine contains 195 vials with 5 full doses per vial (975 doses per pack). It is supplied with 0.9% sodium chloride diluent for injection plastic ampoules.

The full dose of Moderna COVID-19 vaccine (used for primary schedules) is 100 µg of mRNA in 0.5ml of the diluted vaccine. A half dose is 50 µg contained in 0.25ml of the diluted vaccine and is currently the standard booster for this vaccine in the US, UK and AU. A fractional dose will be 20 µg contained in 0.1 ml of the diluted vaccine. Each pack of the Moderna vaccine contains 10 vials with 20 half doses or 50 fractional doses per vial and is a white to off white dispersion.

